# **12. STATISTICAL CONSIDERATIONS**

## **12.1 Statistical Design**

Patient characteristics including demographics, medical history, and concomitant medications will be summarized. The summaries will be done using descriptive statistics, eg, mean, standard deviation, median, minimum and maximum for quantitative values and counts and percents for qualitative variables.

The primary efficacy analysis of flare-free survival in Period 2 from Week 16 to Week 28 will use the intention-to-treat (ITT) population and will be assessed with Kaplan-Meier methods. **Patients will be considered to have flared in Period 2 if they receive rescue medication including increased glucocorticoids, or if they discontinue the study treatment in order to start a different immunosuppressive therapy.**

For Period 1, secondary endpoint variables will be treated as continuous and the values at Week 16 will be compared to Baseline values using Wilcoxon signed-rank tests. The number of patients in glucocorticoid-free remission at week 16 will be reported. Patients will be considered non-responders in Period 1 if they are unable to complete the glucocorticoid taper, receive rescue medication including increased glucocorticoids, or discontinue the study treatment in order to start a different therapy. For Period 1 secondary efficacy endpoints, non-responders will be included in the analysis only if their prednisone dose is equal to or less than the starting dose and stable for the 4 weeks preceding Week 16. The rationale for this is that patients who flare despite sarilumab therapy might be given high doses of steroids, thus improving their endpoints and falsely attributing the success to sarilumab. As a sensitivity analysis, we will also assess the secondary outcomes using the baseline observation carried forward (BOCF) for those patients deemed non-responders.

For Period 2, time to first flare will be compared using a 2-sided log-rank test. The proportion of patients in glucocorticoid-free remission at week 28 in sarilumab-treated patients compared to placebo controls will be analyzed using a Fisher's exact test. The remaining secondary endpoint variables will be treated as continuous and the values at Week 28 will be compared to Week 16 and to Baseline values using Wilcoxon signed-rank tests. We will not perform any corrections for multiple hypothesis testing due to the exploratory nature of this pilot study which solely aims to generate areas of potential future investigation.

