## 12.3 Sample Size

The sample size for Period 1 of the trial of 15 patients was calculated based on the assumption that 80% of the patients will respond to open-label sarilumab, allowing for 12 patients to enroll in the randomized withdrawal Period 2 of the study. The sample size of 12 for Period 2 was calculated based on the assumption that 85% of the placebo group (roughly 5 out of 6) will flare (i.e. require reinitiation of prednisone) over the subsequent 12 weeks compared to 15% (roughly 1 out of 6) in the sarilumab group. This relative hazard of 0.20 gives a power of 80% with an alpha of 0.05 to detect a difference between treatment groups assuming Kaplan-Meier analysis. There is no published data on the use of sarilumab in sarcoidosis on which to base these assumptions. However, a parallel can be drawn between glucocorticoid-dependent sarcoidosis and glucocorticoid-dependent recurrent pericarditis, as they are both inflammatory and refractory to typical treatments. The latter condition has been studied with Anakinra, an interleukin 1 $\beta$  recombinant receptor antagonist [19]. In that study, 21 out of 21 patients (100%) had a complete response in Period 1 and were subsequently randomized to withdrawal during Period 2. In Period 2, 9 out of 10 (90%) patients receiving placebo had disease recurrence compared to 2 out of 11 patients (18%) receiving Anakinra. Although this is a different disease with a drug targeting a different inflammatory cytokine, there is precedent for a dramatic response in diseases like sarcoidosis using drugs like sarilumab. A sample size of 15 was deemed recruitable at Stanford after searching the Stanford medicine Research data Repository (STARR), which is a clinical data warehouse containing all patients seen at Stanford Hospital and Clinics. A search for patients between the ages of 18 and 75 who were given the diagnosis code for sarcoidosis on at least two separate occasions within the last year and who are currently on prednisone, yields 200 potential patients. Assuming half of these are coded correctly, and one-third of those truly have glucocorticoid-dependent, refractory disease, that leaves roughly 30 patients to screen, half of which we anticipate will be eligible for, and willing to participate in, the study. Our IRB will allow us to identify specific patients within STARR whom we can contact to determine their interest in the study.

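### The BOCF sensitivity analysis for Period 1 gives non-responders a change of zero, which the planned signed-rank test discards, so its p-value cannot show whether the Week 16 secondary results are robust to treatment failures

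*Combined protocol and SAP*

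**What the plan says.** All points are in Section 12.1 (Statistical Design) unless noted.

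- **Test.** For the Period 1 secondary endpoints, "the values at Week 16 will be compared to Baseline values using Wilcoxon signed-rank tests".
- **Who is a non-responder.** "Patients will be considered non-responders in Period 1 if they are unable to complete the glucocorticoid taper". Receiving rescue medication, or stopping study treatment to start another therapy, also counts.
- **Main analysis.** "non-responders will be included in the analysis only if their prednisone dose is equal to or less than the starting dose", and only if that dose was stable over the last 4 weeks before Week 16. The reason given is that steroids used to treat a flare could raise the scores, "thus improving their endpoints and falsely attributing the success to sarilumab".
- **Sensitivity analysis.** "we will also assess the secondary outcomes using the baseline observation carried forward (BOCF) for those patients deemed non-responders". No other test, no rule for zero differences and no estimate of change is named for it.
- **Expected numbers (Section 12.3).** "80% of the patients will respond to open-label sarilumab, allowing for 12 patients to enroll in the randomized withdrawal Period 2", out of 15 treated.
- **Multiplicity.** "We will not perform any corrections for multiple hypothesis testing due to the exploratory nature of this pilot study".

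The plan also reports how many patients are in glucocorticoid-free remission at Week 16.

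**The concern.** The main analysis leaves out non-responders whose steroid dose is raised or unstable. A sensitivity analysis that puts every non-responder back would normally show whether the result depends on leaving them out. Here the imputation and the test cancel each other. BOCF sets the change to zero, and the signed-rank test removes zeros before it ranks anything. The failures are put back and then dropped again, together with any dose-stable non-responders whom the main analysis had kept.

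Period 1 has no control group, so agreement between the main and BOCF p-values is likely to be read as robustness. That agreement would carry no information about the failures. Change in prednisone dose shows this most clearly. A responder has completed the taper, so the change is a reduction. A non-responder whose dose rose above baseline is excluded from the main test and set to zero in the BOCF test, so an increase can enter neither.

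**Working it through.** **Plan's own figure.** 15 × 0.80 = 12 responders, as Section 12.3 states. This leaves 15 − 12 = 3 non-responders, hence 3 BOCF zeros per endpoint. The individual changes used below are assumed for illustration, because the documents give none.

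**Mechanism.** Under BOCF, the change is Baseline − Baseline = 0. The standard test drops zeros, ranks the absolute values of the n remaining changes, and sums the ranks of improvements (W+) and worsenings (W−). The exact two-sided p is 2 × (sign patterns whose rank sum is at most the smaller of W+ and W−) / 2^n. A non-responder enters neither the ranks nor n, so the BOCF p-value equals the responders-only p-value for any data.

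**Example A: 12 responders and 3 failures.** Ten responders improve, and the two smallest changes are worsenings.

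- BOCF, zeros dropped: n = 12, W− = 1 + 2 = 3, W+ = 78 − 3 = 75. Five subsets of the ranks 1 to 12 sum to 3 or less (none, 1, 2, 3, and 1 with 2). p = 2 × 5 / 4,096 = 0.0024, the same as with the failures deleted.
- BOCF, Pratt: the zeros take ranks 1 to 3 and are then dropped, so the worsenings have ranks 4 and 5 and W− = 9. Eight subsets of the ranks 4 to 15 sum to 9 or less. p = 2 × 8 / 4,096 = 0.0039.
- Failures ranked worst: ranks 13, 14 and 15 join the worsenings, so W− = 3 + 42 = 45 and W+ = 75. Enumerating 2^15 = 32,768 sign patterns gives p = 0.42.

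**Example B: 6 responders, all improving, and 9 failures.**

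- BOCF, zeros dropped: p = 2 / 2^6 = 0.031. Exact Pratt is also 2 / 64 = 0.031, since only one pattern in each tail is as extreme. 9 of 15 (60%) failed.
- Failures ranked worst and tied: W+ = 21, W− = 9 × 11 = 99, p = 0.021, now against the drug.

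**Example C: BOCF against the main analysis.** Twelve responders have changes −9, −8, −7, −6, −5.5, −5, −4, −3, −2, −1, +2.5 and +3.5, where negative is better. The worsenings have ranks 3 and 5, sum 8. Twenty-five subsets sum to 8 or less, so p = 50 / 4,096 = 0.012. Now add one dose-stable non-responder, whom the main analysis keeps.

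| Observed change of that patient | Main analysis | BOCF |
|---|---|---|
| Worsens by 4.5 (rank 7; worsening sum 15; 268 / 8,192) | 0.033 | 0.012 |
| Improves by 4.5 (worsening sum stays 8; 50 / 8,192) | 0.006 | 0.012 |

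BOCF can therefore be less or more conservative than the main analysis. If no non-responder meets the dose rule, the two p-values are identical.

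**Estimates do move.** In Example C without the added patient, putting in 3 zeros takes the median change from −4.5 to −3.0. The signed-rank p-value stays at 0.012.

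**The case against.** The strongest defence is that BOCF does what Section 12.1 wants: a patient rescued with steroids earns the drug no credit. That is true. Counting failures as harm is also a different question from giving them no credit, and for a laboratory value it assumes a lot. But the main rule already withholds credit from patients on raised steroids by excluding them. What the sensitivity analysis could add is the failures' weight, and the test removes it.

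Four stronger readings are tempting, and the documents do not support them.

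- *A reader might infer that failures would go unseen.* They would not. The Week 16 remission count is reported, so 6 responders of 15 would be visible. A median that includes the zeros would also shrink, although Section 12.1 does not plan one for this analysis. Neither of these corrects the test.
- *A reader might infer that BOCF is always less conservative than the main analysis.* Example C shows that it can go either way.
- *A reader might infer that BOCF itself inflates the false-positive rate.* Any inflation comes from dropping failures in general, which the main rule also does for patients on raised steroids. Its size would depend on an assumed link between failing and worsening that the documents do not give.
- *A reader might infer that Pratt ranking makes matters worse.* A normal approximation gives 0.015 in Example B, but the exact value is 0.031. In Example A, Pratt moves slightly against the drug.

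It is also fair to say that these endpoints are exploratory and unadjusted. That limits the consequence. It does not make the check informative.

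**Conclusion.** The concern holds for the p-value of the BOCF sensitivity analysis. With the test the plan names and the usual deletion of zeros, that p-value equals a responders-only p-value whatever happened to the failures. This rests on the definition of the test and not on assumed data. The plan states no zero rule, and exact Pratt ranking makes little difference (0.0039 instead of 0.0024; 0.031 either way).

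The gap between 0.0024 and 0.42 at the plan's expected 12 and 3 illustrates the scale. It depends on the assumed changes and on ranking failures worst, so it is not a forecast.

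The reach is limited to exploratory Week 16 secondary endpoints. The Period 2 flare-free survival analysis does not use BOCF and is unaffected. The wording should be changed before the data are analysed, because a failure-sensitive analysis added later would be post hoc.

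**What to change.** In Section 12.1, keep the main Period 1 analysis and stop using the BOCF signed-rank p-value as the robustness check. Instead:

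1. For each secondary endpoint, report over all treated patients (a) the number improved out of 15, counting non-responders as not improved, and (b) the median change with the BOCF zeros included. Item (a) needs a stated direction of improvement. Section 10.1 gives none for some laboratory measures, such as 25-OH vitamin D, IgG and calcium.
2. For endpoints with a defined direction of benefit (for example ePOST, the VAS scores, FACIT-F, HAQ and prednisone dose), add a signed-rank sensitivity test over all treated patients, with non-responders ranked as worse than any observed worsening. Report the direction of the result.
3. Where a value from an unscheduled visit before rescue exists, it may replace the worst rank. The study calendar (Section 9) lists ePOST, VAS, FACIT-F, HAQ and the sarcoidosis laboratory tests at such visits. It does not list pulmonary function tests, CT, or CK, aldolase and LDH, and it does not guarantee a visit before rescue.

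Items 1 and 2 cost only SAP wording, and item 3 uses values that happen to exist. The downside is that sensitivity results will look less favourable. Worst-ranking can also be significant against the drug when failures are the majority, as in Example B (p = 0.021), which is why the direction must be reported.

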	
reduced to 40 mg daily by the end of week 3 at the clinician's discretion. Starting at week 4, all patients will begin a scheduled prednisone taper that will take place from week 4 until week 16.
 
Patients will be required to adhere to this tapering protocol. If a violation in the tapering schedule occurs, the patient will be deemed a nonresponder. Patients will be required to fill out a daily steroid diary to clearly document their daily prednisone intake. All attempts will be made to perform a pill count at each visit.
 
During Period 2 of the study (starting at Week 16), the patients that responded in Period 1 will be randomized to withdraw from sarilumab. Patients will be assigned in a blinded, 1:1 fashion to receive either sarilumab 200mg subcutaneously every two weeks or matching placebo.

SAMPLE SIZE	15 patients
STATISTICAL CONSIDERATIONS	
The sample size for Period 1 of the trial of 15 patients was calculated based on the assumption that 80% of the patients will respond to open-label sarilumab, allowing for 12 patients to enroll in the randomized withdrawal Period 2 of the study. The sample size of 12 for Period 2 was calculated based on the assumption that 85% of the placebo group (roughly 5 out of 6) will flare (i.e., require reinitiation of prednisone) over the subsequent 12 weeks compared to 15% (roughly 1 out of 6) in the sarilumab group. This relative hazard of 0.20 gives a power of 80% with an alpha of 0.05 to detect a difference between treatment groups assuming Kaplan-Meier analysis.
 
A sample size of 15 was deemed recruitable at Stanford after searching the Stanford medicine Research data Repository (STARR), which is a clinical data warehouse containing all patients seen at Stanford Hospital and Clinics. A search for patients

between the ages of 18 and 75 who were given the diagnosis code for sarcoidosis on at least two separate occasions within the last year and who are currently on prednisone, yields 200 potential patients. Assuming half of these are coded correctly, and one-third of those truly have glucocorticoid-dependent, refractory disease, that leaves roughly 30 patients to screen, half of which we anticipate will be eligible for, and willing to participate in, the study. Our IRB will allow us to identify specific patients within STARR whom we can contact to determine their interest in the study.

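### Section 12.1 names a log-rank test for about 12 patients without a small-sample p-value method; the usual chi-square version has a true error of about 7%, not 5%, if both arms flare at the planned placebo rate

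*Combined protocol and SAP*

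**What the plan says.** Section 12.1 states that the primary analysis of flare-free survival in Period 2 "will use the intention-to-treat (ITT) population and will be assessed with Kaplan-Meier methods", and that "time to first flare will be compared using a 2-sided log-rank test". Section 10.1 lists time to flare as a secondary endpoint, but this log-rank test is the only between-arm test in 12.1 that matches the primary flare-free survival comparison. No reference distribution is given for it, whether chi-square, exact or permutation. For the Week 28 remission proportion, the same section does name an exact test (Fisher's).

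Section 12.3 plans for 80% of 15 patients to respond, "allowing for 12 patients to enroll in the randomized withdrawal Period 2 of the study". It assumes that "85% of the placebo group (roughly 5 out of 6) will flare" over 12 weeks, "compared to 15% (roughly 1 out of 6) in the sarilumab group", and concludes: "This relative hazard of 0.20 gives a power of 80% with an alpha of 0.05 to detect a difference between treatment groups". The Synopsis says "Patients will be assigned in a blinded, 1:1 fashion". Sections 3.4 and 12.2 assign odd random numbers to sarilumab and even ones to placebo and mention no blocking, so a 6:6 split is not assured.

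**The concern.** With no further instruction, a log-rank p-value is normally read from the chi-square distribution with one degree of freedom. That is a large-sample approximation, and with six patients per arm it can be poor. If sarilumab does nothing, the most natural null in this plan is that both arms flare at the assumed placebo rate of 85%. If the test rejects more than 5% of the time there, it does not deliver the alpha that section 12.3 states. With so few flares, a borderline result can also turn on which p-value method is used, and the plan leaves that choice open until after the data are seen.

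**Working it through.** **The plan's own figure.** Schoenfeld's formula with all 12 patients counted as events and a relative hazard of 0.20: √(12 × 0.25) × |ln 0.20| − 1.96 = 1.732 × 1.609 − 1.96 = 0.828, and Φ(0.828) = 79.6%. This matches the stated 80%. The 85% and 15% rates imply only about six flares (6 × 0.85 + 6 × 0.15 = 6); with six events the same formula gives 50.4%. The power question is separate, but it shows that the plan's figure rests on a large-sample formula.

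**Inputs.** From 12.3: 12 patients, 85% placebo flare rate, alpha 0.05. From 12.1: two-sided log-rank. Assumptions not in the documents: the chi-square cut-off of 3.84, untied flare times, no dropout before Week 28, and a common null flare rate, shown over a range.

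**True size at 6:6.** Under the null all C(12,6) = 924 allocations are equally likely. With untied times and common censoring at Week 28, the log-rank statistic depends only on the order of the flares and their number d. For each d, count the allocations rejected, then weight by the Binomial(12, 0.85) probability of d. No shape for the flare-time distribution is needed.

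| d | P(d) at 85% | chi-square rejects | mid-p permutation rejects |
|---|---|---|---|
| 4 | 0.0001 | 56/924 = 6.06% | 56/924 = 6.06% |
| 5 | 0.0006 | 14/924 = 1.52% | 56/924 = 6.06% |
| 6 | 0.0040 | 74/924 = 8.01% | 50/924 = 5.41% |
| 7 | 0.0193 | 44/924 = 4.76% | 44/924 = 4.76% |
| 8 | 0.0683 | 54/924 = 5.84% | 48/924 = 5.19% |
| 9 | 0.1720 | 64/924 = 6.93% | 46/924 = 4.98% |
| 10 to 12 | 0.7358 | 68/924 = 7.36% | 46/924 = 4.98% |

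With three or fewer flares neither version rejects. For chi-square, d = 4 to 6 contribute 0.03 points in total, so the sum is 0.03 + 0.0193 × 4.76 + 0.0683 × 5.84 + 0.1720 × 6.93 + 0.7358 × 7.36 = 0.03 + 0.09 + 0.40 + 1.19 + 5.42 = **7.13%**. The same weighting gives **4.99%** for mid-p. Here mid-p = P(S > s) + ½P(S = s) over the allocations, where S is the log-rank chi-square statistic and s its observed value.

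**Other common flare rates, 6:6.**

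| Rate in both arms | chi-square | mid-p |
|---|---|---|
| 30% | 2.5% | 3.0% |
| 50% | 4.97% | 5.04% |
| 70% | 6.35% | 5.06% |
| 85% | 7.13% | 4.99% |
| 95% | 7.35% | 4.98% |

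The chi-square version exceeds 5% once the common rate passes about 50%; its maximum is 7.36%. The mid-p maximum at 6:6 is 5.14%, at a rate of about 58%.

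**Unequal arms at 85%.** Chances are for simple randomisation of 12, with either arm the larger (for 7:5, 2 × 792/4096).

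| Split | Chance | chi-square | mid-p |
|---|---|---|---|
| 6:6 | 22.6% | 7.1% | 5.0% |
| 7:5 | 38.7% | 6.9% | 5.0% |
| 8:4 | 24.2% | 7.3% | 5.0% |
| 9:3 | 10.7% | 8.2% | 5.1% |

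Over all flare rates and these four splits, mid-p peaks at about 5.3% (at 7:5).

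**Flares dated to visits.** If flares are recorded only at Weeks 18, 20, 24 and 28, ties pull the chi-square size at 6:6 and 85% down to about 5.6-6.0% in simulation, with mid-p at about 4.6-4.9%.

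**Power at 6:6** (400,000 simulated trials, exponential times).

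| Alternative | chi-square | mid-p | ordinary permutation p |
|---|---|---|---|
| 85% v 15% | 76.5% | 75.1% | 63.8% |
| Relative hazard 0.20, placebo 85% | 52.9% | 50.1% | 44.7% |

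Mid-p costs 76.5 − 75.1 = 1.4 points and 52.9 − 50.1 = 2.8 points. The ordinary permutation p-value, whose size never exceeds 4.98% at 6:6, costs 12.7 and 8.2 points.

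**The case against.** The strongest reply has four parts.

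- **The plan never says chi-square.** This stands. A reader might infer that the documents specify an asymptotic test; they do not. The fault is an unstated small-sample method, and the 7.1% belongs to the default reading.
- **The excess is not universal.** This also stands. It is absent at a 50% flare rate, reverses below that, and shrinks if flares are dated to visits. Section 12.3 itself concedes that no sarilumab data in sarcoidosis support its rates. Against that, 85% is the rate the plan chose, and the daily steroid diary in the Synopsis and the unscheduled visits in section 9 make finer dating plausible.
- **Mid-p does not guarantee 5%.** Correct. At 6:6 it reaches about 6% given four or five events, and at 5:7 it reaches 8.1% given four. Under an 85% null such counts are very unlikely, since 12 × 0.85 = 10.2 flares are expected. Strict control needs the ordinary permutation p-value and its larger loss of power.
- **This is an exploratory pilot.** Section 12.1 says so, and section 2.2 disclaims use for a new indication. That limits the consequences. But 12.1 uses the exploratory label to justify omitting multiplicity correction; it does not withdraw the 0.05 in section 12.3.

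Two stronger readings are tempting and fail. One is that imbalance from the odd/even scheme steadily worsens the error: the commonest unequal split, 7:5, gives 6.9%, below 6:6, and only 9:3 shows a clear rise. The other is that the planned comparison is invalid: an excess of about two points under one null does not support that.

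**Conclusion.** The point holds in limited form. The plan names a log-rank test for about 12 patients and does not say how its p-value is obtained. On the usual chi-square reading with untied times, the true two-sided error under the plan's own 85% placebo rate is 7.1% at 6:6 and between 6.9% and 8.2% over splits from 7:5 to 9:3, against a stated 5%. With visit-dated flares it is about 5.6-6.0% at 6:6. Mid-p permutation brings the error close to 5% for about 1 to 3 points of power. The size figures rest on no dropout before Week 28 and a common flare rate, and those for untied times are exact under these conditions. The power figures also assume exponential flare times and a 6:6 split. This is a cheap improvement worth making before unblinding, not a fatal flaw.

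**What to change.** Add one sentence to section 12.1: the two-sided p-value for time to first flare is taken from the permutation distribution of the log-rank statistic over all allocations with the realised arm sizes (924 at 6:6), using the mid-p convention. Keep the Kaplan-Meier curves for display. State there that mid-p controls the error approximately and not strictly.

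No extra patients, visits or data are needed. The cost is about 1.4 points of power at 85% v 15% and about 3 points at a relative hazard of 0.20. If the sponsor wants a strict guarantee, the ordinary permutation p-value gives it at about 8-13 points of power; that is not recommended here.

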## 12.2 Randomization

In Period 2 of the study, patients will be randomized to sarilumab or matching placebo. This will be done by our administrative assistant [name]. This will be done using a computer-generated random number. An odd number will be assigned to sarilumab and an even number will be assigned to placebo. Only [name] will be aware of the assignment and she will communicate this directly to the pharmacy. The investigators and patients will remain blinded.

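### Fisher's exact test for Week 28 remission is valid but needlessly conservative at about 6 per arm; a prespecified Boschloo test is never less powerful and keeps size within 5%

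*Combined protocol and SAP*

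**What the plan says.** Section 12.1 gives two between-arm efficacy comparisons for Period 2. For the first, "time to first flare will be compared using a 2-sided log-rank test". For the second, the Week 28 proportion in glucocorticoid-free remission on sarilumab "compared to placebo controls will be analyzed using a Fisher's exact test". No sidedness is stated for the second. Section 10.1 lists it among the additional secondary endpoints. Section 12.1 applies no multiplicity correction and calls the study an exploratory pilot.

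Section 12.3 supplies the planning case. Period 1 enrolls 15 patients with an assumed 80% response, "allowing for 12 patients to enroll in the randomized withdrawal Period 2 of the study". It then assumes that "85% of the placebo group (roughly 5 out of 6) will flare", "compared to 15% (roughly 1 out of 6) in the sarilumab group". The power statement, "This relative hazard of 0.20 gives a power of 80% with an alpha of 0.05 to detect a difference between treatment groups", concerns the time-to-flare comparison. No power is given for the Fisher test.

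The Synopsis gives the allocation: "Patients will be assigned in a blinded, 1:1 fashion to receive either sarilumab 200mg subcutaneously every two weeks or matching placebo". Section 12.2 gives the mechanism: "An odd number will be assigned to sarilumab and an even number will be assigned to placebo". No blocking is described.

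**The concern.** With two arms of about 6, few tables are possible and the distribution of Fisher's test is very coarse. Its true type I error can fall far below the nominal 5%, and power falls with it. The planning result itself, 5 of 6 in remission against 1 of 6, does not reach two-sided significance. Exact unconditional tests use more of the permitted error rate without exceeding it. For a study meant to find leads for later work, missing a real signal is the costlier mistake. The test also has to be chosen before the data are seen, because a switch made after observing p = 0.080 would not be credible.

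**Working it through.** **The plan's own figure.** The 80% in 12.3 is for time to flare. Schoenfeld's formula, power = Φ(|ln HR|·√d / 2 − 1.96), gives 79.6% with HR = 0.20 and d = 12 events. The stated flare rates predict 6 × 0.85 + 6 × 0.15 = 6 events, which gives 50.4%. That is a separate matter. It is noted only to show that 80% does not describe the remission test.

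**Inputs.** 6 per arm (12.3 and Synopsis); remission probabilities 0.85 and 0.15 (the complements of the flare rates in 12.3); alpha 0.05 (12.3). Assumptions: the test is two-sided, flare-free equals remission at Week 28, and there is no dropout.

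**Fisher, 5/6 versus 1/6.** With 6 remissions among 12 patients, the one-tail probability is [C(6,5)·C(6,1) + 1] / C(12,6) = 37/924 = 0.040. The two-sided p is 74/924 = 0.080. In the expected direction, Fisher rejects only for 6 v 0, 6 v 1 and 5 v 0.

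**Boschloo, same table.** This test ranks tables by their Fisher p-value and takes the largest null probability, over the common remission rate, of a table at least as extreme. At 6:6 the maximum for this table is at a rate of 0.5, where a table (a, b) has probability C(6,a)·C(6,b)/4096. The tables in one direction are 6v0, 6v1, 5v0, 5v1, 6v2 and 4v0, with weights 1 + 6 + 6 + 36 + 15 + 15 = 79. So p = 2 × 79/4096 = 0.0386, and all six tables reject.

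**Maximum size at 6:6.** Fisher: 2 × (1 + 6 + 6)/4096 = 0.63%. Boschloo: 3.86%.

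**Power at 6:6, 85% versus 15%.**
- Pr(6v0) = 0.1422; Pr(6v1) = Pr(5v0) = 0.1506. Fisher: 0.1422 + 2 × 0.1506 = 44.3%.
- Adding Pr(5v1) = 0.1595 and Pr(6v2) = Pr(4v0) = 0.0664 each gives Boschloo 73.6%.
- At exactly 5/6 versus 1/6, the figures are 38.1% and 67.7%.

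**Other splits, 85% versus 15%, by full enumeration.**

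| Split | Fisher | Boschloo | Gain (points) |
|---|---|---|---|
| 6:6 | 44.3% | 73.6% | 29.2 |
| 7:5 | 58.1% | 73.6% | 15.5 |
| 8:4 | 44.3% | 70.9% | 26.6 |
| 9:3 | 60.3% | 60.3% | 0 |
| 5:6 | 49.2% | 62.3% | 13.0 |
| 5:5 | 54.4% | 54.4% | 0 |
| 6:7 | 69.2% | 72.9% | 4 |
| 7:7 | 64.8% | 68.7% | 4.0 |

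**Averages.** Unrestricted odd/even allocation of 12 patients gives 6:6 with probability C(12,6)/4096 = 22.6%. Averaged over all splits of 12, power is 50.9% for Fisher and 70.7% for Boschloo, a gain of 19.7 points. If the number of responders is also Binomial(15, 0.8), the averages are 55.0% and 66.4%, a gain of about 11 points.

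In every split enumerated, Boschloo's power was at least Fisher's and its size was at or below 5%.

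**The case against.** Fisher's test is valid and conventional at this size, and the choice between conditional and unconditional exact inference is an old debate. The endpoint is an exploratory secondary one, no power was claimed for it, and nearly the same contrast is already examined by the log-rank test (simulated power 76.9% at 6 per arm, 85% versus 15%, exponential times). All of this stands, and it is why the point concerns efficiency. It does not make the choice a trade-off: in the splits enumerated, Boschloo loses no power and stays within the permitted error rate. The actual error rate does rise towards 5%, and no multiplicity correction is planned, but that is the rate the plan already accepts.

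Two assumptions also matter. If Fisher's test were one-sided at 0.05, p would be 0.040 and power 73.6% at 6:6, and the problem there would vanish. The two-sided reading is inferred from the log-rank sentence in the same section. And 5/6 and 1/6 are flare rates; a patient could flare, taper again and be off prednisone at Week 28.

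A reader might infer that, if sarilumab works as assumed, the Fisher result will most likely be non-significant, or that a gain of 30 points is to be expected. The documents support neither. Both hold at 6:6, but exactly 12 responders has probability 25.0% under the 80% assumption and a 6:6 split 22.6% given 12, so the two together have a chance of about 5.6%. Averaged over splits of 12, Fisher rejects 51% of the time, and 55% when responder numbers also vary.

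**Conclusion.** The point holds as an avoidable loss of power. In the planned 6:6 case, Fisher's test misses the plan's own expected table (0.080 against 0.039) and has 44% power against 74%. Over the ways the trial could unfold, the expected gain from Boschloo is about 11 to 20 points, and it is zero in some splits. These figures rest on a two-sided 0.05 test, on treating flare-free as remission, on true rates of 85% and 15%, on no dropout and, for the averages, on unblocked allocation. It would be wrong to read this as showing that Fisher's test is invalid or that the primary analysis is impaired.

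**What to change.** In 12.1, replace Fisher's exact test for Week 28 remission with a two-sided Boschloo exact unconditional test at 0.05. Report the risk difference with an exact unconditional 95% CI; the plan names no effect estimate for this comparison. State how the two-sided p-value is formed. The figures above rank tables by the two-sided Fisher p-value. Software that doubles a one-sided p-value gives the same result at 6:6 but a smaller gain at 8:4.

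The cost is a sentence or two in the SAP and the use of standard software. No patients, visits or data are added, and the wording should be settled before unblinding.
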